7.2.3. Action taken and outcome

The Investigator will record the action taken with drug and outcome of the event for each AE according to the following:

Action taken with investigational drug

- Drug permanently withdrawn – in case a patient is permanently withdrawn from the study drug
- Drug temporarily withdrawn – in case the study drug is temporarily withdrawn
- Dose not changed – in case no action is taken regarding the study drug
- Unknown
- Not applicable – an AE started before initiation of treatment with study drug, the treatment had been completed prior to reaction/event, or the patient has died.

Outcome

- Recovered/resolved

- Recovering/resolving
- Not recovered/not resolved
- Recovered/resolved with sequelae
- Fatal
- Unknown.

Note: In case of irreversible congenital anomalies the choice not recovered/not resolved should be used. “Fatal” should be used when death is possibly related to the reaction/event.

7.3. Reporting

7.3.1. Reporting an adverse event

All AEs regardless of seriousness or relationship to study drug, including those occurring during the Screening Period, are to be recorded on the corresponding page(s) of the eCRF and in the patient’s medical record from the ICF signature until study end for each patient. Whenever possible, symptoms should be grouped as a single syndrome or diagnosis. The Investigator should specify the date of onset, maximal intensity, action taken with respect to study drug, corrective therapy given, outcome, and his/her opinion as to whether there is a reasonable possibility that the AE was caused by the study drug.

Adverse event reporting begins from signature of the patient ICF at the first Screening Visit and ends at study end for each patient.

7.3.2. Initial reports

All SAEs occurring from the time of informed consent until 30 days following the last administration of study drug must be reported to Medpace Clinical Safety within 24 hours of the knowledge of the occurrence (this refers to any adverse event that meets any of the aforementioned serious criteria). All SAEs that the Investigator considers related to study drug occurring after the 30-day follow-up period must be reported to the Sponsor.

To report the SAE, complete the SAE form electronically in the electronic data capture (EDC) system for the study. When the form is completed, Medpace Safety

personnel will be notified electronically and will retrieve the form. If the event meets serious criteria and it is not possible to access the EDC system, send an email to Medpace Safety at [contact] or call the Medpace SAE hotline (phone number listed below), and fax the completed paper SAE form to Medpace (fax number listed below) within 24 hours of awareness. When the EDC system becomes available, the SAE information must be entered within 24 hours of the system becoming available.

7.3.3. Follow-up reports

The Investigator must continue to follow the patient until the SAE has subsided or until the condition becomes chronic in nature, stabilizes (in the case of persistent impairment), or the patient dies.

Within 24 hours of receipt of follow-up information, the Investigator must update the SAE form electronically in the EDC system for the study and submit any supporting documentation (eg, patient discharge summary or autopsy reports) to Medpace Clinical Safety via fax or e-mail. If it is not possible to access the EDC system, refer to the procedures outlined above for initial reporting of SAEs.

All SAEs independent of the circumstances or suspected cause must be reported on a SAE Form/captured in EDC. The SAE Form should include a clearly written narrative describing signs, symptoms, and treatment of the event, diagnostic procedures, as well as any relevant laboratory data and any sequelae, in order to allow a complete medical assessment of the case and independent determination of the possible causality.

It is critical that the information provided on the initial or follow-up SAE Form matches the information recorded in the source documents and the eCRF for the same event.

Any unexpected safety issue that changes the risk benefit analysis and is likely to have an impact on the patients who have participated in the trial will be reported as soon as possible to the Competent Authority(ies) concerned together with proposed actions.

7.3.4. Follow-up

The Investigator should take all appropriate measures to ensure the safety of the patients, notably he/she should follow up the outcome of any AE until the return to normal or until stabilization of the patient's condition.

The patient must be followed up until clinical recovery is complete and laboratory results have returned to normal, or until progression has been stabilized. This information should be documented in the patient's medical records.

7.4. Post Study Reporting Requirements

Any SAEs and deaths that occur within 30 days of the last dose of the study drug, regardless of causality, should be reported.

Any SAE that is brought to the attention of the Investigator at any time after the reporting period and which is considered by him/her to be caused by the study drug within a reasonable possibility, should be reported.

7.5. Special Situation Reports

Special situations reports include pregnancy reports, reports of medication error, abuse, misuse or overdose, and reports associated with product complaints.

7.5.1. Pregnancy

In case of pregnancy, the Investigator will notify regulatory authorities and IRB within 24 hours of his/her knowledge of the pregnancy.

Female patients must be instructed to discontinue the study drug immediately and inform the Investigator as soon as possible once they are aware of being pregnant or suspect that they are pregnant during the study or within 30 days of the last dose of the study drug.

Female patients will be requested, as part of the general ICF, to provide informed consent to allow reasonable attempts to be made to obtain information on any possible medicinal product exposure to an embryo or fetus and to follow up on the outcome of the pregnancy.

The Investigator will contact the patient at the expected time of delivery for follow-up.

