4.2. Inclusion Criteria

Patients must meet all of the following inclusion criteria to be eligible for enrollment in the trial:

1. Males or females aged from 18 to 75 years inclusive the Screening Visit.
2. Must provide signed written informed consent and agree to comply with the study protocol.
3. Females participating in this study must be of non-childbearing potential or using highly efficient contraception for the full duration of the study. Childbearing potential refers to those female subjects who have not had a hysterectomy, bilateral oophorectomy, or medically-documented ovarian failure. Female subjects are considered postmenopausal and not of child-bearing potential if they are >55 years of age, or >50 years of age with >12 months of amenorrhea, or have serum follicle stimulating hormone (FSH) values >40 mIU/ml with >12 months of amenorrhea. Highly efficient contraception is defined as the use of one of the

following methods of birth control in addition to a male partner using a condom (unless surgically sterile) from Screening to 90 days after the last dose of study medication:

- hormone-containing contraceptive
 - intrauterine device
 - cervical cap or diaphragm with spermicidal agent
4. Histological confirmation of steatohepatitis on a diagnostic liver biopsy (biopsy obtained within 6 months prior to Screening or during the Screening Period) with at least 1 in each component of the NAS (steatosis scored 0-3, ballooning degeneration scored 0-2, and lobular inflammation scored 0-3).
 5. Fibrosis stage of 2 or 3, according to the NASH CRN fibrosis staging system on a diagnostic liver biopsy (biopsy obtained within 6 months prior to Screening or during the Screening Period).
 6. Two assessments of ALT, AST, Total bilirubin, ALP, CPK will be collected during screening at least 4 weeks apart. To be eligible the second value cannot be $\geq 2x$ the first value.

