7.1.3. Serious Adverse Events

A serious adverse event (SAE) is defined as an event that, at any dose, results in the following:

- Death
- Life-threatening (Note: The term “life-threatening” in the definition of “serious” refers to an event in which the subject was at risk of death at the time of the event; it does not refer to an event that hypothetically might have caused death if it were more severe.)
- In-patient hospitalization or prolongation of existing hospitalization
- Persistent or significant disability/incapacity
- A congenital anomaly/birth defect
- A medically important event or reaction: such events may not be immediately life-threatening or result in death or hospitalization but may jeopardize the subject or may require intervention to prevent one of the

other outcomes constituting SAEs. Medical and scientific judgment must be exercised to determine whether such an event is a reportable under expedited reporting rules. Examples of medically important events include intensive treatment in an emergency room or at home for allergic bronchospasm; blood dyscrasias or convulsions that do not result in hospitalization; and development of drug dependency or drug abuse. For the avoidance of doubt, infections resulting from contaminated medicinal product will be considered a medically important event and subject to expedited reporting requirements.

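### Contraception is required to 90 days after the last dose, but the protocol's instruction to patients to report a pregnancy stops at 30 days

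*Protocol*

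**What the plan says.** **Contraception.** Inclusion criterion 3, in the synopsis and in protocol section 4.2, requires highly efficient contraception "from Screening to 90 days after the last dose of study medication".

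**Patient's duty to report.** Section 7.5.1 tells female patients to stop the drug at once and inform the Investigator as soon as they are aware of a pregnancy or "suspect that they are pregnant during the study or within 30 days of the last dose of the study drug".

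**Investigator's duties once informed.** Under section 7.5.1 the authorities and IRB are notified "within 24 hours of his/her knowledge of the pregnancy". On outcome, "The Investigator will contact the patient at the expected time of delivery for follow-up". Patients are asked to agree to follow-up of fetal exposure and pregnancy outcome "as part of the general ICF". None of these duties has an end date.

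**SAE windows.** Section 7.3.2 sets the routine window: "All SAEs occurring from the time of informed consent until 30 days following the last administration of study drug". Section 7.4 keeps reporting open after that for an SAE that the Investigator attributes to the drug and that is "brought to the attention of the Investigator at any time after the reporting period". Section 7.1.3 lists "A congenital anomaly/birth defect" as an SAE criterion.

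**Last tests.** Women of childbearing potential have a urine pregnancy test at the end-of-study visit, 4 weeks after treatment ± 3 days (section 6.5.1). Those who leave early have one at the early termination visit (section 6.5.2).

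**The concern.** The protocol asks a woman to avoid pregnancy for 90 days after her last dose but to report one for only 30. It gives no reason for the difference. If contraception fails in the remaining 60 days, nothing in the protocol text prompts her to tell the Investigator, and no further visit or test is scheduled.

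The later steps all begin with the Investigator's knowledge. The 24-hour notification runs from that knowledge, and contact at delivery presupposes it. Late reporting of a birth defect attributed to the drug needs the event to reach the Investigator. The instruction to the patient is the step meant to supply that knowledge, and it is the step that stops early.

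The stake is completeness of pregnancy reporting in a safety study. No primary or secondary analysis is involved.

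**Working it through.** The plan states no figure to reproduce. The check sets the windows side by side and bounds the likely number of events.

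**1. Gap between the windows.** Inputs: 90 days (section 4.2) and 30 days (section 7.5.1).
90 − 30 = 60 days, that is, days 31 to 90 after the last dose.

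**2. Does the phrase covering the study itself close the gap for a completer?** Take the last dose at the Week 24 visit, Day 169.
- End-of-study visit: 169 + 28 = Day 197.
- End of the 30-day instruction: 169 + 30 = Day 199.
- End of required contraception: 169 + 90 = Day 259.

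The 30-day limit reaches 30 − 28 = 2 days past the end-of-study visit. With the visit at 25 to 31 days, the reach is 30 − 25 = 5 days to 30 − 31 = −1 day. In that last case the study itself carries the instruction to day 31, and the gap is 90 − 31 = 59 days. So being in the study adds at most a day.

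**3. Who is affected.**
- Completers: the end-of-study test should pick up conceptions on treatment. Assume that a urine test turns positive 10 to 21 days after conception (not in the documents). For conception on the day of the last dose and the earliest visit, 25 − 21 = 4 days remain to spare. What is left is mostly conception after dosing.
- Women who stop the drug but stay on the visit schedule (section 6.6.3): still covered while in the study.
- Women who leave at or near their last dose: the final test may be the early termination test. If it falls on the day of the last dose, it would miss conceptions in the preceding 10 to 21 days under the same assumption.

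**4. Two readings of the 30-day clause.**
- The limit attaches to being pregnant: a pregnancy that exists by day 30 and is recognised on, say, day 40 is covered.
- The limit attaches to becoming aware or suspecting: the same pregnancy is not covered, and this could include a late on-treatment conception in a woman who left early.

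The sentence supports either reading.

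**5. Expected pregnancies in the 60 days.** Formula: women of childbearing potential × pregnancies per woman-year × 60/365. The documents give 20 subjects of both sexes. The rest is assumed: 1 to 10 such women, and 1% to 10% per woman-year.

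| Case | Calculation | Expected |
|---|---|---|
| Low | 1 × 0.01 × 60/365 | 0.002 |
| High | 10 × 0.10 × 60/365 | 0.16 |
| Unrealistic ceiling, all 20 subjects | 20 × 0.10 × 60/365 | 0.33 |

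**The case against.** **The windows serve different purposes.** One limits conception and the other triggers reporting. Nothing in the documents requires them to be equal, and 30 days matches the SAE window. This stands: a reader might infer a contradiction, and there is none. Aligning the windows is good practice.

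**Exposure is not shown.** A reader might infer that a fetus conceived in days 31 to 90 would be exposed to the drug. Section 1.2.2 gives the time to peak concentration and the excretion routes, but no half-life. The documents contain no reproductive-toxicity data and do not explain the choice of 90 days, which may simply be a cautious margin. This also stands.

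**Late-recognised pregnancies may be covered.** A reader might infer that an on-treatment conception recognised after day 30 is certainly excluded. That holds on only one of the two readings. The duty also starts on suspicion, so a negative early termination test does not end it. What remains is an ambiguity.

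**The Investigator's duties stay open.** A pregnancy that comes to light after day 30 would still be notified and followed up, and a birth defect attributed to the drug is reportable at any time. This is true, but none of these duties prompts the patient.

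**The consent form may already deal with it.** Patients would ordinarily meet this instruction there, and that form was not available. If it covers 90 days, the practical gap closes and only the protocol wording is out of step.

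**The numbers are tiny.** They are, and that limits the importance of the point without removing the gap.

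**Conclusion.** The point holds as a minor one. On the protocol text, contraception is required for 60 days beyond the end of the instruction to report a pregnancy, and no other part of the protocol or SAP extends that instruction. In that period the Investigator learns of a contraceptive failure only if the patient volunteers it. The clause is also ambiguous about late recognition, which matters most for women who leave early.

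Well under one event is expected: 0.002 to 0.16 on assumed numbers of women and assumed pregnancy rates. No analysis, eligibility rule or dosing decision changes. The conclusion does not depend on drug exposure in days 31 to 90 or on any conflict between the two windows. Its practical weight depends on the consent form.

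**What to change.** In section 7.5.1, change the limit on the patient's instruction from 30 to 90 days after the last dose. Put the same limit in the consent form if it is not already there. Leave the 90-day contraception requirement and the 30-day SAE window unchanged.

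This also settles most of the ambiguity in practice: on either reading, a late on-treatment conception recognised by day 90 would be covered.

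The cost is one changed number in the protocol, possibly a matching line in the consent form, and a slightly longer pregnancy-reporting period. No visits or tests are added. Section 9.11 requires IRB/IEC approval before a change takes effect, so the edit would have to form part of an approved amendment.

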7.5.2. Medication error

Medication error is defined as an unintentional error in the prescribing, dispensing, or administration of a medicinal product while in the control of the healthcare professional, patient, or consumer. All medication errors will be documented in the eCRF and, in case of any potential risk to patient safety, would be reported as appropriate.

7.5.3. Misuse

This refers to situations where the medicinal product is intentionally and inappropriately used not in accordance with the authorized product information and will be reported in the eCRF. All misuse will be documented in the eCRF and, in case of any potential risk to patient safety, would be reported as appropriate.

7.5.4. Overdose

This refers to the administration of a quantity of a medicinal product given per administration or cumulatively, which is above the maximum recommended dose according to the authorized product information. Clinical judgment should always be applied. Doses >4000 mg in one day are considered overdose.

7.5.5. Abuse

This corresponds to the persistent or sporadic, intentional excessive use of a medicinal product, which is accompanied by harmful physical or psychological effects.

8. Statistical Considerations

This section is an overview of the principal elements of the statistical analysis for this study. Further details will be contained in a separate statistical analysis plan (SAP).

8.1. Analysis Endpoints

8.1.1. Primary Endpoint

The primary endpoint is to assess the safety and tolerability of NTZ after 24 weeks of treatment

8.1.2. Secondary Endpoints

The secondary endpoints are:

- To assess the % change in FSR from baseline to end of treatment (24 weeks of treatment)
- To assess the change in liver stiffness by MRE from baseline to 12 weeks and 24 weeks of treatment
- To assess the change in liver stiffness by fibroscan from baseline to 24 weeks of treatment
- To assess the change from baseline to 12 weeks and 24 weeks of treatment of fibrosis serum biomarkers and scores

8.2. Analysis Sets

The Full Analysis Set will consist of all subjects that meet the eligibility criteria and enroll into the study (Visit 1 Day 1).

The Safety Set will consist of all enrolled subjects who receive at least one dose of study drug.

8.3. Data Handling Conventions

Continuous variables will be summarized with descriptive statistics (i.e., sample size, mean, standard deviation, minimum, maximum, median, and quintiles). Categorical variables will be summarized with descriptive statistics (i.e., sample size, frequency counts, and percentage). Statistical testing on change from baseline values will be performed using analysis of variance techniques with a term for baseline in the model. Statistical significance will be considered to have been reached at an alpha level of 0.05.

Baseline value is measured on Day 1 of the treatment period before the administration of NTZ.

8.4. Demographic Data and Baseline Characteristics

Demographic and baseline characteristics will be descriptively summarized. Quantitative and/or categorical summaries will be presented for demographics and other baseline characteristics. Demographic and baseline characteristics will be summarized using the Full Analysis Set.

8.5. Primary Safety Analysis

Safety and tolerability will be assessed by the following parameters:

AEs including TEAEs and SAEs, laboratory evaluations, vital signs, ECGs, and physical examinations.

8.5.1. Adverse Events

Treatment-emergent adverse events (TEAEs) are defined as AEs that worsen or commence on or after the time of start of first study drug administration. AEs, including SAEs, will be coded using MedDRA. The number and percentage of subjects experiencing TEAE, including TEAEs leading to study drug discontinuation and SAEs, will be summarized for each system organ class (SOC) and Preferred Term. In addition, AEs will be tabulated according to severity, causality, and relation to the study drug.

Individual data listings for AEs will be presented for each subject.

8.5.2. Laboratory Evaluations

Absolute and change from baseline values for laboratory parameters will be summarized by visit. In addition, shift from baseline tables will be presented for selected laboratory abnormalities.

8.5.3. Other Safety Evaluations

Observed values and change from baseline will be summarized descriptively for all vital sign parameters and ECG parameters by visit. Individual listings will be presented for each subject. Individual data listings for physical examination results will be presented for each subject.

Safety data will be summarized using descriptive statistics. Further details will be provided in the SAP.

All safety analyses will be conducted using the Safety Population.

8.6. Secondary Efficacy Analyses

8.6.1. FSR

Fractional Synthesis Rate of circulating plasma proteins will be measured at Baseline, and after 24 weeks of treatment.

The change in FSR (absolute and relative) from baseline to end of treatment between the first and second deuterated water loading periods will be assessed to determine the effects of NTZ 500mg BID on de novo collagen synthesis in the Full Analysis Set.

Wilcoxon signed-rank test will be used for statistical inference. Estimated mean, standard error and 95% confidence interval of change in FSR (absolute and relative) change from baseline in FSR will be reported and evaluated at a significance level of 0.05. Exploratory analyses may also be performed to evaluate the association of individual exploratory biomarkers or combination of biomarkers with clinical measurements and other risk factors.

Additional details will be provided in the SAP.

8.6.2. Liver stiffness

The change in liver stiffness from baseline at 24 weeks as measured by FibroScan, and at 12 weeks and 24 weeks by MRE, the change in non-invasive markers of fibrosis from baseline to 24 weeks, and the change in fibrosis scores from baseline to 12 weeks, to 24 weeks for the Full Analysis Set will be assessed. Summary statistics for the Full Analysis Set will be provided at all visits and the change from baseline will be provided.

8.6.3. Exploratory Analysis

Additional serum and plasma samples will be maintained for future analysis. Exploratory measures for MRI/MRE sequence development will be maintained for future analysis.

8.6.4. Interim Analysis

An interim analysis is not planned.

8.7. Sample Size

The sample size of this Phase 2 proof of concept study is based on clinical assessment. Twenty male and female subjects with histologically confirmed NASH and fibrosis stage 2 or 3) will provide sufficient information to assess the safety and tolerability of NTZ 500mg BID over 24 weeks.

9. Responsibilities

